6.3. Changes From Protocol-Specified Efficacy Analyses

FibroTest measurements were not specified to be collected at Week 24 in the study protocol but were collected in the study. FibroTest analyses were updated to include the Week 24 measurement.

7. SAFETY ANALYSES

For the final analysis, cumulative safety data (treatment-emergent AEs, treatment-emergent laboratory abnormalities, etc.) will be summarized for (1) subjects in the FAS during the double-blind phase, (2) subjects in the Open-Label Safety Analysis Set during the open-label phase, and (3) subjects in the TFFU Safety Analysis Set during the TFFU phase. Exposure data will be summarized for (1) and (2).

By-visit summary tables of safety measurements will be presented for the entire study treatment period (double-blind and open-label phase combined) based on subjects in the Safety Analysis Set from baseline to Week 96, and open-label phase based on subjects in the Open-Label Safety Analysis Set from open-label baseline to Week 96. Statistical comparisons will only be performed for the analysis of the entire study treatment period, unless otherwise specified. No by-visit summaries for safety measurements will be generated for the TFFU phase.

All safety data including data collected during the treatment-free follow-up period will be included in data listings.

7.1. Adverse Events

7.1.1. Adverse Event Dictionary

AEs will be coded using the Medical Dictionary for Regulatory Activities (MedDRA). System Organ Class (SOC), high-level group term (HLGT), high-level term (HLT), preferred term (PT), and lower-level term (LLT) will be attached to the clinical database.

7.1.2. Adverse Event Severity

Adverse events are graded by the investigator as Grade 1 (mild), Grade 2 (moderate), Grade 3 (severe) or Grade 4 (life threatening) according to toxicity criteria specified in Appendix 4 of the clinical study protocol. The severity grade of events for which the investigator did not record severity will be categorized as "missing" for tabular summaries and data listings, and will be considered the least severe for the purposes of sorting for data presentation.

7.1.3. Relationship of AEs to Study Drug

Related AEs are those for which the investigator answers "Yes" to the question "Related to Study Treatment?" in the eCRF. Events for which the investigator did not record relationship to study drug will be considered related to study drug for summary purpose. Data listings will show relationship as missing.

7.1.4. Relationship of AEs to Study Procedure

AEs for which 'Yes' is marked for question 'Related to Study Procedures?' in the eCRF will be identified and included in AE listing.

7.1.5. Serious AEs

Serious AEs (SAEs) are those identified as serious in the eCRF, where 'Yes' was marked for 'AE serious'. The clinical database will be reconciled with the SAE database (from the Pharmacovigilance and Epidemiology [PVE] Department) before database finalization.

7.1.6. Treatment-Emergent AEs

7.1.6.1. Definition of Treatment-Emergent

Treatment-emergent AEs will be separately defined for the double-blind phase and the open-label phase. Post-treatment-emergent AEs will be defined only for the TFFU phase.

Treatment-emergent AEs occurring during the double-blind phase are defined as:

- Any AE with onset date on or after the blinded study drug start date and no later than the minimum of the blinded study drug stop date + 3 days and the day prior to the first dose date of open-label study drug, if applicable, for those who discontinued blinded study drug permanently, or
- Any AE with onset date on or after the blinded study drug start date for those who are still on the blinded study drug, or
- Any AE leading to blinded study drug discontinuation.

Treatment-emergent AEs occurring during the open-label phase are defined as:

- Any AE with onset date on or after the open-label study drug start date and no later than the open-label study drug stop date + 3 days for those who discontinued open-label study drug permanently, or
- Any AE with onset date on or after the open-label study drug start date for those who are still on open-label study drug, or
- Any AE leading to open-label study drug discontinuation.

Post-treatment-emergent AEs occurring during the TFFU phase are defined as:

Any AE with onset date after the last dose of study drug + 3 days

7.1.6.2. Incomplete Dates

If an AE onset date is incomplete or completely missing, the following rules will be used to determine if the AE is considered treatment emergent during the double-blind and open-label phases, or post-treatment-emergent during the TFFU phase:

Events with Missing Onset Day and/or Month

The event is treatment-emergent during the double-blind phase if the following criteria are met:

- The month and year (or year) of onset date is the same as or after the month and year (or year) of the first dose of the blinded study drug, and
- For those who discontinued the blinded study drug permanently only: the month and year (or year) of onset date is the same as or before the month and year (or year) of the date of the minimum of the blinded study drug stop date + 3 days and the day prior to the first dose date of open-label study drug, if applicable, and
- AE end date is as follows:

The (complete) end date is on or after the first dose date of the blinded study drug, or

The month and year (or year) of end date is the same or after the month and year (or year) of the first dose of the blinded study drug, or

End date is completely missing

The event is treatment-emergent during the open-label phase if the following criteria are met:

- The month and year (or year) of onset date is the same as or after the month and year (or year) of the first dose of the open-label study drug, and
- For those who discontinued the blinded study drug permanently only: the month and year (or year) of onset date is the same as or before the month and year (or year) of the date of the last dose of the open-label study drug + 3 days, and
- AE end date is as follows:

The (complete) end date is on or after the first dose date of the open-label study drug, or

The month and year (or year) of end date is the same or after the month and year (or year) of the first dose of the open-label study drug, or

End date is completely missing

The event is post-treatment-emergent during the TFFU phase if the following criteria are met:

• The month and year (or year) of onset date is the same as or after the month and year (or year) of the day after the last dose date + 3 days

Events with Completely Missing Onset Date

An AE with a completely missing onset date is defined as treatment-emergent AE during the double-blind phase if end date is as follows:

- The (complete) end date is on or after the first dose date of the blinded study drug, or
- The month and year (or year) of end date is the same or after the month and year (or year) of the first dose of the blinded study drug, or
- End date is completely missing

An AE with a completely missing onset date is defined as treatment-emergent AE during the open-label phase if end date is as follows:

- The (complete) end date is on or after the first dose date of the open-label study drug, or
- The month and year (or year) of end date is the same or after the month and year (or year) of the first dose of the open-label study drug, or
- End date is completely missing

The event is post-treatment-emergent during the TFFU phase if the following criteria are met:

- The (complete) end date is after the last dose date + 3 days, or
- The month and year (or year) of end date is the same or after the month and year (or year) of the day after the last dose date + 3 days, or
- End date is completely missing

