7.1.7. Summaries of AEs and Deaths

AEs will be summarized for (1) subjects in the Safety Analysis Set during the double-blind phase, (2) subjects in the Open-Label Safety Analysis Set during the open-label phase, and (3) subjects in the TFFU Safety Analysis Set during the TFFU phase. The full set of AE summaries as described below will be generated for (1) and (2).

A brief summary of AEs (ie, the number and percentage of subjects) will be presented by treatment group for the following: any treatment-emergent AE, any Grade 3 or 4 treatment-emergent AE, any Grade 2, 3 or 4 treatment-emergent AE, any treatment-emergent study drug-related AE, any Grade 2, 3 or 4 treatment-emergent study drug-related AE, any Grade 2, 3 or 4 treatment-emergent study drug-related AE, any treatment-emergent serious adverse event (SAE),

any treatment-emergent study drug-related SAE, any treatment-emergent AE leading to premature study drug discontinuation, any treatment-emergent AE leading to dose modification or study drug interruption, and any death.

Summaries (number and percentage of subjects) of AEs (by SOC, HLT [if specified below], and PT) will be provided by treatment group and overall as follows:

- All treatment-emergent AEs summarized by SOC, HLT, and PT
- Any Grade 3 or 4 treatment-emergent AEs
- Any Grade 2, 3, or 4 treatment-emergent AEs
- All treatment-emergent nonserious AEs occurring in at least 5% of subjects in any treatment group (this summary is generated per requirement for reporting in ClinicalTrials.gov)
- All treatment-emergent study drug-related AEs summarized by SOC, HLT, and PT
- Any Grade 3 or 4 treatment-emergent study drug-related AEs
- Any Grade 2, 3, or 4 treatment-emergent study drug-related AEs
- All treatment-emergent SAEs
- All treatment-emergent study drug-related SAEs
- All treatment-emergent AEs leading to premature discontinuation from study drug
- All treatment-emergent AEs leading to dose modification or study drug interruption

Multiple events will be counted once only per subject in each summary. For data presentation, SOC (and HLT) will be ordered alphabetically, with PT sorted by decreasing total frequency. For summaries by severity grade, the most severe event will be selected.

For post-treatment AEs during the TFFU phase, the overall summary and individual summaries will be provided only for the following:

- All post-treatment-emergent AEs
- Any Grade 3 and 4 post-treatment-emergent AEs
- All post-treatment-emergent SAEs

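### The SAP's follow-up-phase rule for AEs with a partial onset date has no end-date check, so some AEs recorded as ending by last dose + 3 days are classed as post-treatment-emergent

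*SAP*

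**What the plan says.** SAP Section 7.1.6.1 sets the target for the TFFU phase: "Any AE with onset date after the last dose of study drug + 3 days".

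Section 7.1.6.2 then covers incomplete onset dates.

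- **Onset day and/or month missing.** The double-blind and open-label rules each combine a condition on onset with a condition on the end date. The first end-date alternative is "The (complete) end date is on or after the first dose date of the blinded study drug, or" for the double-blind phase and "The (complete) end date is on or after the first dose date of the open-label study drug, or" for the open-label phase. The TFFU rule has one criterion only: the onset month and year (or year) "is the same as or after the month and year (or year) of the day after the last dose date + 3 days".
- **Onset date completely missing.** All three rules rest on the end date. The double-blind rule opens with "An AE with a completely missing onset date is defined as treatment-emergent AE during the double-blind phase if end date is as follows", and the open-label rule has the same form. The first alternative for TFFU is "The (complete) end date is after the last dose date + 3 days, or".

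Section 7.1.7 uses the TFFU classification for an overall summary and three individual ones: "All post-treatment-emergent AEs", the Grade 3 and 4 subset, and SAEs.

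**The concern.** The SAP checks the end date when it knows nothing about onset and drops the check when it knows the month or year. A known end date can settle the question on its own: an AE that was over by last dose + 3 days did not start later than that. Under the partial-onset TFFU rule this information is ignored, no reason is given, and no other part of the SAP restores the check.

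At stake is who is counted as having an off-treatment AE, Grade 3 or 4 AE, or SAE. The error runs one way, because it can only move on-treatment events into the off-treatment tables. Those tables may rest on few subjects and few genuine events. Protocol Section 3.1 encourages alternative HBV therapy, and starting it ends the off-treatment follow-up. Protocol Section 7.3 collects AEs other than SAEs only until 30 days after the last dose.

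**Working it through.** The plan states no figure on this point, so there is none to reproduce. The check sets the six rules side by side, runs the partial-onset TFFU rule on examples, and then bounds the size.

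**1. Rules compared (SAP 7.1.6.2)**

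| Onset information | Double-blind | Open-label | TFFU |
|---|---|---|---|
| Partial | onset and end date | onset and end date | onset only |
| Completely missing | end date | end date | end date |

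In the two on-treatment partial-date rules, the end-date condition removes AEs that were over before the phase began. The TFFU phase also has a starting point (last dose + 4 days), but its partial-date rule has no such condition.

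**2. Examples (illustrative dates; LDD = last dose date)**

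| LDD | LDD + 4 | Recorded onset | Recorded end | TFFU rule as written | With end date required after LDD + 3 |
|---|---|---|---|---|---|
| 20 Jun 2019 | 24 Jun 2019 | Jun 2019 | 10 Jun 2019 | counted | not counted |
| 20 Jun 2019 | 24 Jun 2019 | 2019 | 10 Feb 2019 | counted | not counted |
| 29 Jun 2019 | 3 Jul 2019 | Jun 2019 | any | not counted | not counted |

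Rows 1 and 2 contradict Section 7.1.6.1. With an assumed open-label start of 20 Jul 2018, the row 1 AE also meets the open-label rule, so it appears in both phases. Row 3 shows the limit of the problem: the recorded onset must fall in the same month (or year) as LDD + 4. A later onset month or year cannot go with an end date by LDD + 3.

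**3. How often the calendar condition is met**

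- LDD and LDD + 4 fall in the same month unless LDD is one of the last four days of a month: 365 − 12 × 4 = 317 of 365 days.
- They fall in the same year on 365 − 4 = 361 of 365 days.

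**4. Size for month-and-year onsets**

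The documents give neither the number of TFFU subjects nor the frequency of partial dates. Assumed inputs:

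- TFFU subjects per arm: 10 to 50
- AE rate: 1.5 per subject-year
- share of AEs with partial onset: 3 to 10%

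Partial-onset AEs in the calendar month of the last dose, per arm:

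- low: 10 × 1.5 × 0.03 × 1/12 = 0.0375
- high: 50 × 1.5 × 0.10 × 1/12 = 0.625

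Only those that ended by LDD + 3 are misplaced. Take a 30-day month, an evenly spread last-dose day d, one-day AEs and complete end dates. Then d must be 26 or lower for LDD + 4 to stay in the month, a fraction of 26/30. For those days, the mean share of the month up to d + 3 is (13.5 + 3)/30 = 0.55. The product is 0.55 × 26/30 = 0.48.

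- low: 0.0375 × 0.48 = 0.018
- high: 0.625 × 0.48 = 0.30

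That is about 0.02 to 0.3 AEs per arm. It is an upper figure on these inputs, because longer AEs or missing end dates reduce it. Year-only onsets would add to it, since the matching period is a year and not a month. No figure is given for them, as the documents do not say how often only the year is known.

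**5. Effect on a rate**

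One misplaced subject moves an arm's TFFU rate by 1/50 to 1/10, or 2 to 10 percentage points.

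**The case against.** The strongest reply is that the SAP deliberately leans towards inclusion. When timing is unknown, an AE may count in more than one phase. An onset in March with last dose on 20 March and no end date meets both the open-label and the TFFU rule, and an AE with both dates completely missing meets all three phase rules. That stands as a description of the convention, and the gap is not the only source of double counting. It does not defend the gap, because here a recorded end date settles the timing.

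A reader might infer that any partial-onset AE that ended before the last dose is misplaced. The documents do not support that. An onset in January with last dose on 20 March of the same year is excluded as written, as is the third example above. The subject must also belong to the TFFU Safety Analysis Set (SAP 3.1.4).

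A reader might also take 0.04 to 0.6 AEs per arm as the size, by counting every partial-onset AE in the last-dose month. That includes AEs that did not end by last dose + 3 days, so about half should be removed. The rate shift is conditional too: SAP 7.1.7 counts a subject once per summary, so a misplaced AE changes a rate only if that subject has no genuine TFFU AE in the table.

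Safeguards make the case rarer, above all for SAEs. Sites record AE start and end dates (Protocol 9.1.5), discrepancies are queried (9.1.6), SAEs are transmitted within 24 hours of the investigator's knowledge (7.3), and they are reconciled with the safety database (SAP 7.1.5). By-subject listings let a misplaced event be traced. These points bear on frequency; they do not correct the rule.

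**Conclusion.** The rule is wrong as written, within a narrow scope. It misclassifies an AE in a TFFU subject when the recorded onset month and year (or year, if that is all that is known) equals that of last dose + 4 days and the recorded end date is on or before last dose + 3 days.

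The likely effect is small: at most about 0.02 to 0.3 AEs per arm for month-and-year onsets, resting entirely on the assumed inputs above. It is always upward. It is confined to descriptive TFFU tables with no hypothesis test, and no primary or key secondary endpoint is touched. The documents give no basis for inferring a material distortion of the SAE or Grade 3 and 4 results. This is a minor correction, worth making because it is unambiguous and nearly free.

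**What to change.** Add an end-date condition to the partial-onset TFFU rule in SAP 7.1.6.2, using the three alternatives already given for TFFU when onset is completely missing. The AE then qualifies only if one of these also holds:

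- a complete end date falls later than last dose + 3 days;
- a partial end date has a month and year (or year) no earlier than that of last dose + 4 days;
- no end date is recorded at all.

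This removes only AEs whose recorded end date rules out a post-treatment onset, so no genuine off-treatment AE is lost. It leaves untouched the double counting that the SAP accepts when timing is unknown.

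The cost is one added condition and the matching program change, with no new data. SAP Section 1 already provides for changes after finalization to be documented in the CSR.

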7.1.7. Summaries of AEs and Deaths

AEs will be summarized for (1) subjects in the Safety Analysis Set during the double-blind phase, (2) subjects in the Open-Label Safety Analysis Set during the open-label phase, and (3) subjects in the TFFU Safety Analysis Set during the TFFU phase. The full set of AE summaries as described below will be generated for (1) and (2).

A brief summary of AEs (ie, the number and percentage of subjects) will be presented by treatment group for the following: any treatment-emergent AE, any Grade 3 or 4 treatment-emergent AE, any Grade 2, 3 or 4 treatment-emergent AE, any treatment-emergent study drug-related AE, any Grade 2, 3 or 4 treatment-emergent study drug-related AE, any Grade 2, 3 or 4 treatment-emergent study drug-related AE, any treatment-emergent serious adverse event (SAE),

any treatment-emergent study drug-related SAE, any treatment-emergent AE leading to premature study drug discontinuation, any treatment-emergent AE leading to dose modification or study drug interruption, and any death.

Summaries (number and percentage of subjects) of AEs (by SOC, HLT [if specified below], and PT) will be provided by treatment group and overall as follows:

- All treatment-emergent AEs summarized by SOC, HLT, and PT
- Any Grade 3 or 4 treatment-emergent AEs
- Any Grade 2, 3, or 4 treatment-emergent AEs
- All treatment-emergent nonserious AEs occurring in at least 5% of subjects in any treatment group (this summary is generated per requirement for reporting in ClinicalTrials.gov)
- All treatment-emergent study drug-related AEs summarized by SOC, HLT, and PT
- Any Grade 3 or 4 treatment-emergent study drug-related AEs
- Any Grade 2, 3, or 4 treatment-emergent study drug-related AEs
- All treatment-emergent SAEs
- All treatment-emergent study drug-related SAEs
- All treatment-emergent AEs leading to premature discontinuation from study drug
- All treatment-emergent AEs leading to dose modification or study drug interruption

Multiple events will be counted once only per subject in each summary. For data presentation, SOC (and HLT) will be ordered alphabetically, with PT sorted by decreasing total frequency. For summaries by severity grade, the most severe event will be selected.

For post-treatment AEs during the TFFU phase, the overall summary and individual summaries will be provided only for the following:

- All post-treatment-emergent AEs
- Any Grade 3 and 4 post-treatment-emergent AEs
- All post-treatment-emergent SAEs

In addition to the by-treatment summaries, data listings will be provided for the following:

• All AEs

- Grade 3 and 4 AEs
- SAEs
- Study drug-related SAEs
- Deaths
- AEs leading to premature discontinuation of study drug
- AEs leading to dose modification or study drug interruption

7.2. Laboratory Evaluations

Laboratory data collected during the study will be analyzed and summarized using both quantitative and qualitative methods. Summaries of laboratory data will be provided for (1) the double-blind phase and open-label phase for subjects in the Safety Analysis Set from baseline to Week 96, and (2) summaries of laboratory data will be provided for the open-label phase only for subjects in the Open-Label Safety Analysis Set from open-label baseline to Week 96. Only laboratory abnormalities will be summarized for subjects in the TFFU Safety Analysis Set from TFFU baseline to the end of study.

The analyses will be based on values reported in conventional units. When values are below the LOQ, they will be listed as such, and the closest imputed value will be used for the purpose of calculating summary statistics as specified in Section 3.5.

A by-subject listing for laboratory test results will be provided by subject ID number and visit in chronological order for hematology, serum chemistry, urine chemistry, and urinalysis separately. Values falling outside of the relevant reference range and/or having a severity grade of 1 or higher on the Gilead Grading Scale for Severity of Adverse Events and Laboratory Abnormalities will be flagged in the data listings, as appropriate.

7.2.1. Summaries of Numeric Laboratory Results

Descriptive statistics (sample size, mean, SD, median, Q1, Q3, minimum, and maximum) will be provided by treatment group for each laboratory test during the double-blind phase and openlabel phase for subjects in the Safety Analysis Set from baseline to Week 96 as follows:

- Baseline values
- Values at each postbaseline analysis window
- Change from baseline to each postbaseline analysis window
- Percentage change from baseline to each postbaseline analysis window (if specified)

A baseline laboratory value will be defined as the last measurement obtained on or prior to the date of first dose of blinded study drug. Change from baseline to a postbaseline visit will be defined as the visit value minus the baseline value.

Descriptive statistics (sample size, mean, SD, median, Q1, Q3, minimum, and maximum) will also be provided by treatment group for each laboratory test during the open-label phase only based on subjects in the Open-Label Safety Analysis Set from open-label baseline to Week 96, as follows:

- Open-label baseline values
- Values at each open-label postbaseline analysis window
- Change from open-label postbaseline to each open-label postbaseline analysis window
- Percentage change from open-label postbaseline to each open-label postbaseline analysis window (if specified)

An open-label baseline laboratory value will be defined as the last measurement obtained on or prior to the date of first dose of open-label study drug. Change from open-label baseline to an open-label postbaseline visit will be defined as the visit value minus the open-label baseline value.

Descriptive summaries for numeric laboratory results measured during the TFFU phase will not be provided.

Mean, median, Q1, Q3, minimum, and maximum values will be displayed to the reported number of digits; SD values will be displayed to the reported number of digits plus 1. In the case of multiple values in an analysis window, data will be selected for analysis as described in Section 3.6.2.

Median (Q1, Q3) change from baseline to Week 96 in selected safety endpoints over time, including the fasting lipid panel parameters and fasting glucose, for subjects in the Safety Analysis Set will be plotted by treatment group. This will be repeated for subjects in the Open-Label Safety Analysis Set from open-label baseline to Week 96.

